### Aims

1. To determine the feasibility, sensitivity and specificity of digital PCR as a method to detect MRD in DS AML (by amplifying each patient's clone-specific *GATA1* mutation) compared to flow cytometry.
2. To determine the feasibility, sensitivity, specificity and cost of targeted, error-corrected sequencing (of a region encompassing exon 2 of *GATA1*) as a method to detect MRD in DS AML compared to digital PCR and flow cytometry.

**Experimental Plan.** DNA will be extracted from the diagnostic bone marrow samples of the patients with DS AML accrued by AAML1531. Of the 240 evaluable patients expected to enroll on AAML1531, 228 (95%) are anticipated to have diagnostic bone marrow available for analysis. Somatic *GATA1* mutations will be determined for all samples. MRD will be measured on Day 28 after the start of the first cycle of induction chemotherapy (Induction I). During this interval, a patient-specific *GATA1* mutation probe will be designed and tested for sensitivity and specificity in serial dilutions of diagnostic bone marrow DNA. Suitable probes will achieve  $>10^{-4}$  *GATA1* mutation-positive blasts in a background of normal bone marrow DNA. In parallel to MRD measurement by multi-dimensional flow cytometry, for patients who consent to this optional study, bone marrow samples obtained on Day 28 will be assessed for MRD by digital PCR (using the prepared probe and standard primer combinations) as well as ECS of exon 2 of *GATA1* (using high-fidelity PCR amplification across the 240 base pair exon, which can be individually barcoded and multiplexed for simultaneous amplification from multiple patients).

**Analysis Plan.** To determine feasibility, the proportion of cases will be recorded for which the design of a sufficiently sensitive primer and probe combination for digital PCR was successful by Day 28. Similarly, the proportion of cases will be determined for which the requirements for DNA quality and multiplex amplification were met. Library preparation, sequencing and bioinformatic analysis will follow previously established protocols. Positive and negative percent agreement of MRD results obtained on Day 28 will be compared between flow cytometry, digital PCR and ECS for each pair of detection methods. Corresponding 95% confidence intervals will be calculated for the percent positive and negative agreement for each pair of detection methods. McNemar's test will be used to compare percent positive and negative agreement for two detection methods relative to the third detection method. MRD results obtained with each method will be correlated with the probability of disease-free survival and the cumulative incidence of relapse.

**Relevance.** This direct comparison of methods is expected to determine the optimal method to measure treatment response by MRD and predict relapse risk in DS AML in the context of risk-based treatment assignment by flow cytometry based MRD. Results, therefore, will establish the foundation of accurate risk-based stratification of treatment intensity for future therapeutic trials in DS AML.

15.1.3 To establish a DS AML cell bank of viably frozen bone marrow samples and corresponding non-tumor DNA samples collected at end of induction.

**Background.** The exploratory aim 1.2.2 is to establish a biobank of viably frozen bone marrow samples from DS AML patients collected at the end of Induction I for future research.

**Experimental Plan.** Bone marrow cells will be collected at end of Induction 1 and viably cryopreserved for those patients who consent to this optional study. Bone marrow samples collected at the time point of MRD analysis, which in the majority of cases will be obtained at the time of morphological remission, will provide non-tumor DNA for genomic analyses of DS AML blasts.

**Relevance.** The repository of viably cryopreserved bone marrow samples of DS AML, remission samples and other sources non-tumor DNA will provide essential support for the objectives of this study and serve as a vital resource for future mechanistic studies in DS AML.

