While MRD measured in the bone marrow by flow cytometry at the end of Induction I is prognostic and provides superior detection of persistent disease compared to morphology alone, this approach does have limitations. On AAML0431, 14 patients relapsed and of the 12 patients for whom MRD data was available, only 7/12 (58%) were MRD positive at the end of Induction I, suggesting that MRD by flow cytometry is unable to detect all high risk patients. The reasons for this may be related to the flow cytometry method used to identify residual clones, namely the leukemia-associated immunophenotype (LAIP) at diagnosis, which is susceptible to immunophenotypic gains or losses in the major clone as well as the emergence of initially undetected minor clones. A newer flow cytometry methodology based on the detection of “different from normal”, which is expected to have improved accuracy and sensitivity, will be employed in the current study. The same methodology is currently used on AAML1031 to detect MRD in non-DS AML. In addition, the proposed study will evaluate alternative DNA-based methods to measure MRD such as digital PCR and targeted sequencing. The presence of clone-specific somatic mutations of the *GATA1* gene in DS AML blasts provides a particularly suitable target for the detection and quantification of MRD for response assessment in clinical trials. Currently there is no validated PCR or sequencing assay that could serve as the gold standard for the quantitative detection of cells harboring clone-specific *GATA1* mutations. The value of these molecular methods to detect MRD in DS AML will be determined in Exploratory Aim 1.2.2.

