### 9.2 Patient Accrual and Expected Duration of Trial

AAML1531 will be compared against a fixed 2-year EFS of 93.5% for SR patients and 76% for HR patients which were observed for comparable patients treated on the prior COG study of DS AML patients (AAML0431). For SR patients, assuming a null EFS of 93.5% at 2 years, there is 95% power to detect an alternative EFS of 87% at 2 years with 1-sided testing at the 10% level of statistical significance if there are 200 SR patients who continue to Induction II. For HR patients, assuming a null EFS of 76% at 2 years, there is 80% power to detect an alternative EFS of 88% at 2 years with 1-sided testing at the 10% level of statistical significance if there are 41 high risk patients who continue to Induction II. The necessary sample size was computed using a binomial test. The final analysis of EFS will occur after a minimum of 2 years after the last patient is enrolled.

\* Replaced with Amendment #6

Up to 3% of patients enrolled are expected to be found ineligible, up to 3% are expected to go off protocol therapy at the end of Induction I, and approximately 83% of patients are expected to be SR. Therefore, enrollment of up to 256 patients will be required to assure that there are 200 SR patients who continue to Induction II and there are 41 HR patients continue to Induction II. Based on an accrual estimate of 60 patients per year, accrual of 256 patients is expected to be completed in approximately 4.3 years.

\* Updated with Amendment #4A

As of October 22, 2018, 26 of the 143 patients enrolled are HR patients who continued to Induction II. Up to 3% of patients enrolled are expected to be found ineligible, up to 3% are expected to go off protocol therapy at the end of Induction I, and approximately 83% of patients are expected to be SR. Therefore, enrollment of up to 256 patients will be required to assure that there are 41 HR patients who continue to Induction II. Based on an accrual estimate of 60 patients per year, accrual of an additional 113 patients is expected to be completed in approximately 2 years.

\* Updated with Amendment #6

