**Methods.** Multi-dimensional flow cytometry has the advantage that it can be performed rapidly, but its sensitivity and specificity is limited in DS AML. Of note, interpretation of flow cytometric MRD data in DS AML is complicated by the observation that normal bone marrow cells in DS may express patterns of surface markers that are absent from normal non-DS bone marrow ([name], personal communication). These patterns must not be confused with evidence of residual leukemia (when defined as marker pattern that is different from normal). DNA-based methods, such as quantitative real time PCR can detect individual patients' clone-specific *GATA1* mutations in exon 2 using either mutation-specific primers (and a shared probe) or a mutation-specific probes (and shared primers) with high sensitivity and specificity but can encounter limitations to feasibility due to constraints on the design of primers and probes in a short exon. Digital PCR technology, with its increased options for primer design, and massively parallel sequencing, which circumvents the constraints of designing mutation-specific oligonucleotide primers and probes, provide promising new approaches to the detect *GATA1* mutations and measure MRD in DS AML.

**Hypotheses.** We hypothesize that measurement of MRD in DS AML by digital PCR to detect clone-specific *GATA1* mutations is feasible and both more sensitive and specific than multi-dimensional flow cytometry. We hypothesize further that

measurement of MRD in DS AML by error-corrected sequencing (ECS) of exon 2 of *GATA1* to detect clone-specific mutations is as sensitive and specific as digital PCR but more cost-effective (since there is no need for mutation-specific primer and probe design). ECS has shown sensitivity for single base substitutions to 1:10,000, validated by digital PCR^61 and comparable to flow cytometry or RT-PCR.

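### The only test named for the hypothesis that sequencing matches digital PCR is McNemar's test for a difference, with no margin, so a non-significant result cannot support it

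*Combined protocol and SAP*

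**What the plan says.** Section 15.1.2 (Hypotheses) makes two claims about MRD measurement at the end of Induction I. Digital PCR for the patient's own GATA1 mutation "is feasible and both more sensitive and specific than multi-dimensional flow cytometry". Error-corrected sequencing "is as sensitive and specific as digital PCR but more cost-effective".

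The Analysis Plan of the same section provides positive and negative percent agreement for each pair of methods, with intervals: "Corresponding 95% confidence intervals will be calculated for the percent positive and negative agreement for each pair of detection methods". For testing it says: "McNemar's test will be used to compare percent positive and negative agreement for two detection methods relative to the third detection method". It also plans to correlate each method's result with disease-free survival and relapse. It states no margin, significance level, form of the test, power or decision rule.

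On a reference standard, Section 2.10.2.2 says: "Currently there is no validated PCR or sequencing assay that could serve as the gold standard". Section 15.0 describes these studies as research only, with no bearing on treatment.

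**The concern.** The sequencing hypothesis is one of equality, or at least of not being worse. McNemar's test takes equality as its null hypothesis and can only produce evidence against it. A non-significant result is what a good assay would give. It is also what a worse assay gives when the sample is small, and it becomes more likely as the sample shrinks.

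The hypothesis that PCR is better than flow has a related difficulty. Agreement with flow cannot show superiority to flow, because a true PCR positive that flow misses is counted as disagreement.

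At stake is the use the section has in mind. It expects this comparison to identify the best MRD method and to underpin risk stratification in later trials.

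**Working it through.** **Inputs from the documents**
- Flow-positive (MRD at or above 0.05%) is the definition of high risk (Sections 3.3.4 and 4.1.5). The power statement in Section 9.2 holds "if there are 41 high risk patients who continue to Induction II".
- Section 9.2 reproduces: 256 × 0.97 × 0.97 = 240.9 evaluable, and 240.9 × 0.17 = 40.9, i.e. 41. After Amendment 6: 32 + 0.10 × 90 = 41.
- Section 15.1.2 expects 228 of 240 evaluable patients (95%) to have diagnostic marrow. On that count the flow-negative group is about 228 − 41 = 187. The 228 corresponds to enrollment of 256, and enrollment has since risen to 312.
- Participation is optional and the consent rate is not stated, so 41 is in effect a ceiling.

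**Assumptions (not in the documents)**
- Two-sided 5% level.
- Positive agreement with flow of 95% for digital PCR and 95% minus the deficit for sequencing.
- Errors either nested (sequencing misses everything PCR misses, plus more) or conditionally independent. The ranges below span these two cases.

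**Step 1: what the exact test needs.** With all m discordant pairs in one direction, p = 2 × 0.5^m. For m = 5, p = 0.0625; for m = 6, p = 0.031. So at least six one-way discordant pairs are needed. At 41 children and a nested 10-point deficit, the power is P(Binomial(41, 0.10) ≥ 6) = 0.223.

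**Step 2: chance of missing a true deficit in positive agreement** (full enumeration)

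| True deficit | n = 41, exact | n = 41, uncorrected | n = 30, exact |
|---|---|---|---|
| 10 points | 78-81% | 40-70% | 90-93% |
| 15 points | 41-59% | 12-48% | 71-75% |
| 20 points | 14-37% | 2-27% | 43-56% |

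At n = 20 the exact test misses a 10-point deficit 97-99% of the time.

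**Step 3: negative agreement.** With 187 flow-negative children, the exact test has 88-100% power for a drop from 95% to 85%, and 37-91% for a drop from 95% to 90%.

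**Step 4: what the planned intervals show.** At n = 41, agreement of 39/41 = 95.1% has a 95% interval of 83.5-99.4%, and 37/41 = 90.2% has 76.9-97.3%. These show the imprecision of each figure. Two such intervals do not give the interval for the difference, because both assays are run on the same children.

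**Step 5: the paired difference at n = 41.** The 95% half-width is 1.96 × √((D − d²)/n), where D is the proportion discordant and d the difference. With D = 0.10 and d = 0 this is 1.96 × √(0.10/41) = 0.097, or ±9.7 points. For an illustrative 10-point margin and no true difference, power is Φ(0.10 × √(41/0.10) − 1.96) = Φ(0.065) = 53%. At D = 0.05 it is 82%, and at D = 0.20 it is 30%. For a 15-point margin and D = 0.10 it is 86%.

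**The case against.** A reader might infer that a clearly worse sequencing assay would usually be declared equal to PCR, and that the plan favors the cheaper method by default. The documents do not support that.

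- Nothing in Section 15.1.2 says a non-significant result will be read as equality.
- McNemar's test is not the only evidence planned. The pairwise intervals include sequencing against digital PCR directly, and that comparison is not confined to flow-positive children.
- Missing a worse assay more often than not depends on the size of the deficit, the form of the test and the numbers. With 41 children it holds at about 10 points with the exact test. It is roughly even at 15 points and false at 20 or more. The plan does not say which form will be used, and the uncorrected form misses less.
- The limit of 41 applies to positive agreement with flow as reference, and not to the specificity half.

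The planned correlation with disease-free survival and relapse is also a sensible response to the lack of a gold standard. It is only partial, since Section 4.1.4 ends data collection on standard risk patients enrolled after Amendment 4A.

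All of this stands, and it limits the point. It does not remove it: the hypothesis is still one of equality, the test is still one for a difference, and no margin says how much agreement would be enough. It is also fair to say that an unpowered exploratory comparison of assays is ordinary practice, which is why calling it descriptive is an acceptable remedy.

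**Conclusion.** The mismatch between hypothesis and test is real but minor. For positive agreement, a non-significant McNemar result is weak evidence, because the exact test at the ceiling of about 41 children misses a 10-point deficit roughly four times in five. For negative agreement the numbers are adequate against a drop of that size, though a non-significant result would still need a margin to be read as equality.

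The sizes rest on the assumed significance level, test form, agreement rates and error dependence. The consent rate is unknown and can only make the positive side worse. The mismatch itself depends on none of these. Because the aim is exploratory and guides no treatment, this is a worthwhile improvement at low cost.

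**What to change.** In the Analysis Plan of Section 15.1.2:

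1. Report the paired sequencing-minus-PCR difference in positive and in negative agreement, each with its 95% confidence interval.
2. Base any statement that sequencing is as sensitive or specific on that interval, against a margin the sponsor sets in advance. Otherwise label the comparison descriptive. State that equality will not be inferred from a non-significant McNemar test.
3. Reword the claim of superiority to flow as agreement with flow, supplemented by the outcome correlation already planned. The dilution series in the Experimental Plan does not fill this gap, because it is described for the GATA1 probes and not for flow.

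The cost is a few sentences and a different summary of the same paired data, with no new samples. The downside is that positive agreement may well end as not shown: at 41 children and an assumed 10% discordance, a 10-point margin would have about 53% power even if the assays were truly equal.

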## 14.0 SPECIAL STUDIES SPECIMEN REQUIREMENTS

### 14.1 Summary of Specimens

Study	Time points	Collection Details	Additional Details	Mailing Destination
MRD Required from all patients	→ Pre-treatment → End of Induction I → End of Induction II (High Risk Patients only)	2-4 mL of anticoagulated bone marrow in sodium heparin (green top tube).  For the Pre-Treatment sample only: If BM sample cannot be obtained, and the peripheral blood has at least 20% blasts, send 5 mL of blood in sodium heparin (green top tube).	Store at room temperature. Ship on the day of collection. If sample is stored for longer than 24 hours, add equal volume of RPMI medium. Do not freeze MRD samples. ( See Section 14.2 )	1 ([name]'s lab) Section 14.2.3
Banking of viable cells (Optional: Patient Consent Required)	→ Pre-treatment → End of Induction I → Relapse	3-10 mL bone marrow into a sterile syringe containing a sterile solution of preservative-free heparin.	Place in a 15 mL sterile conical centrifuge tube and add 5 mL of sterile RPMI-1640 with 20% fetal calf serum. If specimen is not shipped on the day of collection, store in a refrigerator until shipment. ( See Section 14.3 )	2 (Leukemia Biospecimen Bank at BPC) Section 14.3.3
GATA-1 mutation (Optional: Patient Consent Required)	→ Pre-treatment → End of Induction I	2-4 mL bone marrow into an EDTA containing tube (purple top).	If specimen is not shipped on the day of collection, store in a refrigerator until shipment. ( See Section 14.3 )	2 (Leukemia Biospecimen Bank at BPC) Section 14.3.3

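### McNemar's test of each DNA-based MRD assay against flow uses the other DNA assay as reference, so any errors the two share favour the DNA assay; the result cannot support a sensitivity or specificity claim

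*Combined protocol and SAP*

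**What the plan says.** Section 15.1.2 hypothesises that digital PCR "is feasible and both more sensitive and specific than multi-dimensional flow cytometry". The two aims that follow are also worded as feasibility, sensitivity and specificity.

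The Analysis Plan of Section 15.1.2 has three elements that bear on this:
- Positive and negative percent agreement "will be compared between flow cytometry, digital PCR and ECS for each pair of detection methods", with 95% confidence intervals.
- McNemar's test, "used to compare percent positive and negative agreement for two detection methods relative to the third detection method". This is the only test named for comparing methods. No significance level, power or effect size is given for it.
- Correlation of each method's result with disease-free survival and cumulative incidence of relapse. No test or rule for comparing methods on outcome is given.

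On the samples, the Experimental Plan says that Day 28 marrow from consenting patients "will be assessed for MRD by digital PCR (using the prepared probe and standard primer combinations) as well as ECS of exon 2" in the GATA1 gene. Section 14.1 lists one EDTA marrow specimen for the GATA1 work and a separate sodium heparin specimen for flow.

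On the reference, Section 2.10.2.2 states: "Currently there is no validated PCR or sequencing assay that could serve as the gold standard" for quantifying cells with clone-specific GATA1 mutations.

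**The concern.** With three methods, the third method for PCR against flow is ECS, and for ECS against flow it is PCR. In both cases the reference is the sister assay of one of the two methods compared. Agreement with a reference stands in for accuracy only if the reference is correct, or if its errors are unrelated to those of both methods.

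The documents point the other way. Both DNA assays read the patient's GATA1 mutation in the same marrow specimen, and Section 15.1.2 says that ECS was itself validated by digital PCR. Flow fails for different reasons: marker patterns peculiar to Down syndrome marrow (Section 15.1.2) and immunophenotypic change in the clone (Section 2.10.2.2). A DNA assay can then agree better with the other DNA assay because both make the same mistake.

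The protocol expects this comparison to identify the best MRD method and to underpin risk stratification in later trials. A test that leans towards the DNA assays could misdirect that choice.

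**Working it through.** **Inputs from the documents.** The plan's figure reproduces: 240 evaluable × 0.95 = 228 with diagnostic marrow. The 240 matches Section 9.2: 256 × 0.97 × 0.97 = 240.9. Because the Day 28 DNA study is optional, 228 is an upper bound under that target. The MRD-positive share is 14% in the predecessor study (Section 2.10.2.2), 17% under the earlier accrual assumption (100% − 83%) and 10% under Amendment 6 (Section 9.2).

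**Assumptions.** True positive share p = 0.15; the same sensitivity (Se) and specificity (Sp) for all three methods; exact McNemar, two-sided 5%; 114 as the number if half consent. Shared error is modelled by s, the probability that ECS repeats PCR's call; otherwise ECS makes its own call, independent given true status. Flow is independent of both given true status.

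**Expected positive agreement with ECS** (Se 0.80, Sp 0.97):
- P(ECS positive) = p·Se + (1−p)(1−Sp) = 0.1200 + 0.0255 = 0.1455, or 33.2 of 228.
- Flow: [p·Se² + (1−p)(1−Sp)²] / 0.1455 = (0.0960 + 0.0008) / 0.1455 = 66.5%, whatever s is.
- PCR: s + (1−s) × 66.5% = 66.5% at s = 0, 83% at 0.5, 93% at 0.8 and 98% at 0.95.

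PCR and flow are equally accurate here, yet their agreement with ECS separates as s grows.

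**Expected discordant pairs among ECS-positives** (n = 228):
- PCR positive, flow negative: n{p·Se(1−Se)[s+(1−s)Se] + (1−p)(1−Sp)Sp[s+(1−s)(1−Sp)]}.
- PCR negative, flow positive: n(1−s){p·Se²(1−Se) + (1−p)(1−Sp)²Sp}.
- At s = 0 these are 4.5 and 4.5. At s = 0.8 they are 228 × (0.02304 + 0.01994) = 9.8 and 228 × 0.2 × 0.01994 = 0.9.

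**Simulated chance that PCR is declared better than an equally accurate flow assay on positive agreement.** With s = 0 it is about 1% or less in every row. Repeat runs differ by up to about two percentage points.

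| n | Se / Sp | s = 0.5 | s = 0.8 | s = 0.95 |
|---|---|---|---|---|
| 228 | 80% / 97% | 30% | 76% | 93% |
| 228 | 90% / 98% | 12% | 43% | 60% |
| 228 | 95% / 99% | 2% | 8% | 12% |
| 114 | 80% / 97% | 9% | 28% | 42% |
| 114 | 90% / 98% | 2% | 7% | 11% |

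On negative agreement, the first row gives about 25%, 71% and 93%.

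**Checks.**
- If flow is truly better (90% / 98% against 80% / 97% for both DNA assays, s = 0.8, n = 228), PCR is still declared better on at least one measure in about 79% of trials.
- Against a reference that shares no errors with either method (true status, 14% positive), PCR is falsely declared better on either measure in 2.6% of trials (80% / 95%) and 1.4% (90% / 98%).
- PCR against ECS relative to flow is not inflated: 5% or less.

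**The case against.** Five points can be made for the plan.

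1. *It speaks of agreement, not accuracy.* That is proper wording where no gold standard exists, and no rule says that a significant McNemar result proves superiority. This stands as far as it goes. But the hypotheses and aims are about sensitivity and specificity, and this is the only test that could be read as answering them.
2. *Sharing a target is not the same as sharing errors.* Correct: with independent errors the test holds its size. Section 15.1.2 also describes a PCR-specific limit, primer and probe design in a short exon, which sequencing avoids. The degree of sharing is therefore unknown.
3. *Relapse and disease-free survival give an outside yardstick.* They do, and the plan includes them. But no comparison between methods is specified, and the follow-up available for it shrank with Amendment 4A.
4. *The number tested may be well below 228.* Correct: consent is optional, and the table shows how far the rates fall at 114.
5. *The aim is exploratory.* Correct. Section 15.0 keeps these results out of treatment decisions.

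A reader might infer that the test favours the DNA assays by construction, or would confirm the hypothesis whatever the truth. The documents do not support that: the bias needs errors shared given true status, and they give no figure for it. Nor do they say that one DNA extract is split between PCR and ECS; the single EDTA specimen only makes a common source likely.

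**Conclusion.** The concern holds for two of the three McNemar comparisons: PCR against flow relative to ECS, and ECS against flow relative to PCR. In both, shared errors move the result towards the DNA assay, and agreement with the sister assay is not sensitivity or specificity. PCR against ECS relative to flow is not materially affected.

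The direction follows from the design once errors are shared. The size depends on assumed accuracy, assumed sharing and the number who consent, and runs from near nominal to severe. The largest rates belong to less accurate assays with heavy sharing and all 228 patients; they should not be quoted as the expected error rate. The consequence is confined to how an exploratory comparison is read and used in later trials.

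**What to change.** In the Analysis Plan of Section 15.1.2:
- Keep McNemar's test relative to a third method only for PCR against ECS, with flow as the third.
- For PCR or ECS against flow, report only the pairwise positive and negative agreement with 95% confidence intervals already planned. State that agreement with the other DNA assay does not support a claim of higher sensitivity or specificity.
- Base any accuracy claim on the relapse and disease-free survival analysis already planned, and state two limits. Flow determines the treatment arm (Sections 3.3.4, 3.3.5 and 4.1.2), so within an arm the analysis shows only whether a DNA assay adds to flow. Standard-risk patients enrolled after Amendment 4A leave the study without further data (Sections 4.1.4, 8.2 and 9.3.1).
- Do not cite the planned dilution series as evidence on flow. It uses DNA and tests the PCR probe only.

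The cost is wording; no new samples or laboratory work are needed. The price is that superiority of PCR over flow in sensitivity and specificity can no longer be claimed from agreement data.
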